Probiotics were defined by the WHO as those microorganisms that, when administered in adequate amounts, conferred a health benefit for the host¹. This declaration empowered probiotics and paved the way for the research in this field, allowing the rise of a variety of studies in different fields, being the premature infant the population with great advances². Some of these studies demonstrated that in the premature neonate there is a delay in microbiota acquisition, as well as a substantive difference in composition, presenting a decrease in *Lactobacillus* and *Bifidobacterium* (considered protective microorganisms) and a rise in *Enterobacteriaceae*, that contains pathogens such as *Escherichia coli* and *Klebsiella*³. Nevertheless, dysbiosis (disbalance between commensal flora and pathogenic flora that leads to pathology) could entail a dysregulation between proinflammatory factors and protective factors, putting the extreme premature infant at bigger risk of major complications and increasing the mortality⁴. The study of the microbiota in the premature infant and the application of probiotics have encompassed different lines of research in dysbiosis (related to obesity, allergy and breathing problems in early stages of development⁵), however the most studied aspect has been the use of probiotics to prevent necrotising enterocolitis, one of the most severe disease a newborn infant can confront¹⁰. Moreover, although there is still controversy, there has been a clear benefit in the prophylactic use of different strands of probiotics, specially combined, for the prevention and reduction of the incidence of necrotising enterocolitis^{7,8}. Branching from here, we can also find the use of probiotics in prevention of late-onset sepsis, considered the main side effect of probiotics, and neonatal mortality, where evidence has also shown probiotics to have potential benefit, especially those probiotics containing genres *Bifidobacterium* and *Lactobacillus*⁸. For instance, in animal models *Bifidobacterium spp.* has been shown to have a possible antinflammatory effect through the production of cytokines and synthesis of Th2 lymphocytes, as well as regulation IgE. Additionally, production of short chain fatty acids could help maintain intestinal barrier integrity². Seeing these promising results, one has to ask if the effect of probiotics could extend beyond necrotising enterocolitis, late-onset sepsis and mortality, having other effects in the premature infant, specially those

more immature (<32 weeks gestational age) and very low birthweight (<1500g). A premature neonate is daily challenged by many complications and potential sequelae that will affect the rest of their lives. Between these we have the neurodevelopment with effects that extend beyond cerebral palsy, neurosensorial hearing loss and blindness¹¹.

Regarding neurodevelopment, a gut-brain axis has previously been described, connected through neural, endocrine, and immune pathways¹²⁻¹⁴. Microbiota with its ability to process indispensable metabolites, regulate pathogen microbiota and modulating the immune response, by for example reducing intestinal permeability to lipopolysaccharide (pro-inflammatory factor), could have a key role in the gut-brain axis¹⁴. For instance, substances such as brain derived neurotrophic factor, neutrophines o interleukin-6, implicated in neuroinflammation and neurodevelopment, could see themselves modified by changes in microbiota¹⁶. Nevertheless, the brain derived neurotrophic factor, nerve growth factor and neutrophines 3 and 4 promote neuronal survival and diminish apoptosis of central and peripheral nervous system neurones, being vital for the development of the pre and post-natal brain¹⁷⁻¹⁸. Despite everything, unfortunately there is a lack of published evidence, with only 4 studies analysing the effect of probiotics on the neurodevelopment of the premature new-born, without finding a benefit¹⁹⁻²². However, it is important to note that the assessment of neurodevelopment in those studies is limited around the 2 years of follow-up with the use of a Bayley test. Alas, studies such as the EPICure¹¹ have shown that behavioural changes and impairment in neurodevelopment appear beyond the 2 years of age, even in adulthood, being some of these difficulties in learning, psychiatric disorders o attention deficit and hyperactivity disorder, difficult to detect at the age where the majority of the follow-up is discontinued^{23,24}.

Hypothesis

1. The prophylactic use of a combination of probiotics containing *Bifidobacterium bifidum* and *Lactobacillus acidophilus* in premature infants <32 weeks gestation and <1500g could contribute to improving neurodevelopment at 2 years follow-up. Said improvement will be even more evident at 6 years of age, as well as entailing changes in biomarker patterns of neuroplasticity and neuroinflammation at 6 years of age.
2. The said combination of probiotics will contribute to reducing necrotising enterocolitis, late-onset sepsis, intraventricular haemorrhage, and neonatal mortality. Additionally, there will be a reduction in allergy and breathing disorders in early infancy.

Task distribution

Neonatology (BCNatal Hospital Clinic)

- [name] [name]: information of study, recruitment, informed consent. Data collection and sampling. Coordination of neuropsychology team and laboratory. Interviews with families. Maintenance of database and support to rest of researchers. Elaboration of future manuscripts and statistical analysis of data.
- [name]: information of study, recruitment, and informed consent. Data collection and sampling. Coordination and supervision of the project and neuropsychology and laboratory teams. Maintenance of database. Supervision and writing of future manuscripts.
- [name]: information of the study. Neuropsychological assessment of patients at 2 and 6 years of age. Performance of semi structured interviews to families. Coordination and collaboration with other psychologists attached to the Neonatology Services of BCNatal Hospital Clinic.
- [name]: review of protocols and research. Supervision of project and achievement of objectives. Supervision and writing future manuscripts. Coordination of research teams. Support to other teams and services.

- [name]: review of protocols and research. Supervision of project and achievement of objectives. Data quality assessment and statistical data analysis. Supervision and writing of future manuscripts.

Laboratory (IDIBAPS-GRIE):

- [name]: processing and collection of biological samples. Analysis of biomarkers of neuroinflammation and neurodevelopment with kits based on Luminex Multiplex technology of R&D. Analysis of intestinal permeability with ELISA kit of LifeSpan BioSciences (LS-F55511) in serum. Database management of recruited cohorts.
- [name]: processing and collection of biological samples. Analysis of biomarkers of neuroinflammation and neurodevelopment with kits based on Luminex Multiplex technology of R&D. Analysis of intestinal permeability with ELISA kit of LifeSpan BioSciences (LS-F55511) in serum. Database management of recruited cohorts.


3 Objectives and purpose of the study

The objective of the study is to determine the effect of the combination of 2 probiotics (*Bifidobacterium bifidum* NCDO 2203 y *Lactobacillus acidophilus* NCDO 1748) in the neurodevelopment and neuroimage of extreme premature infants less than 32 weeks gestation and under 1500g at 2 years of age, and the neurodevelopment and neuronal plasticity biomarkers at 6 years of age.

Secondarily the incidence of necrotizing enterocolitis, late-onset sepsis, intraventricular haemorrhage and mortality of premature infants will also be assessed comparing those neonates that received probiotics from those that did not. Moreover, growth curves will be considered to determine the moment of "catch-up" (moment where the infant returns to his correspondent growth curves) between the two groups, and to elucidate whether there is any effect from the moment of "catch-up" and neurodevelopment. Finally, there will be a comparison between obesity, asthma, and respiratory disease at 6 years of age.

On the other hand, at 6 years of age there will be an assessment of neurodevelopment biomarkers and neuroplasticity in blood serum to determine changes in expression linked to probiotic administration, and therefore contribute to the enforcement of the existence of a brain-gut axis and its importance in neurodevelopment.

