3.1 Main and secondary variables

- Gestational age, weight, length and head circumference at birth
- Sex
- Multiple gestation

- Gestational pathology (diabetes, preeclampsia, maternal sepsis, placental disease, in vitro fecundation)
- IUGR and degree of IUGR
- Inborn vs Outborn
- Apgar at 5 and 10 minutes
- Antenatal steroids
- Type of delivery (vaginal vs caesarean)
- Coriamnionitis
- Type of feed (breastfeeding, donor milk or formula)
- Duration of breastfeeding
- Necrotising enterocolitis, early and late-onset sepsis, mortality
- Antibiotic use beyond 48 hours of life
- Days of parenteral nutrition
- Days of enteral nutrition
- Days of invasive ventilation, days of non-invasive ventilation, days of oxygen
- Days of stay in intensive care
- Chronic lung disease
- Intraventricular haemorrhage (I-IV)
- Periventricular leukomalacia
- Cranial ultrasound result
- Retinopathy of prematurity
- Neurosensorial hearing loss
- Cerebral palsy
- Colic in early infancy
- Bayley score at 2 years of age
- MRI at 2-3 years of age
- Growth chart
- Moment of “catch-up”
- Childhood diseases (asthma, atopic skin, hospital admissions, allergy,...)
- Need for antibiotics or probiotics during childhood >48 hours
- Weight and height at the assessment
- WISC-V at 6 years
- CBCL 6-18 (Child Behaviour Checklist 6-18)
- BRIEF-2
- Mother tongue
- Parental age
- Cultural level of parents
- Ethnical origin
- Parents work
- Kind of family (single parent, ...)
- Social services requirements
- Need to attend early stimulation centre

4 Study design

Quasi-experimental, sequential, unicentric, cohort study with the performance of neuropsychological tests and biomarkers of neurodevelopment, inflammation, and intestinal permeability.

We estimate an initial phase of 2 years with a comparison at 6 years of age (4 years after start of trial).

5 Enrolment of participants

Infants born below 32 weeks gestational age and birth weight under 1500g cared for at BCNatal Hospital Clínic (tertiary neonatal unit) in Barcelona between January 2014 and December 2019. There will be a 12 month wash out period (year 2017) to alleviate cross contamination of probiotics.

Participants will be contacted via phone (parent/legal guardian) for those that consented to be included for a 6-year assessment and blood sampling. In those cases where contact via phone has not been possible, contact to reference Paediatrician will be sought.

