5.1 Inclusion criteria

Extreme premature infants <32 weeks and <1500g, cared at BCNatal Hospital Clinic during years 2014-2019. Participants will have to survive beyond 7 days of life (moment where the probiotic intervention will be given). Recruitment will start from January 2014 and will last until December 2019.

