5.2 Exclusion criteria

All neonates presenting with suspected congenital anomalies, inborn errors of metabolism, or genetic defects will be excluded. Infants with a suspected syndrome, or who had suffered events beyond the neonatal period, not related to prematurity, that could entail impairment in neurodevelopment (severe cranioencephalic trauma, oncological process, meningitis, or exposure to toxic substances) will also be excluded.

6 Treatment and study calendar

Intervention

Daily dose of 6x10⁹ UFC Infloran® -Berne, Switzerland- (Bifidobacterium bifidum NCDO 2203 and Lactobacillus acidophilus NCDO 1748) from 7 days of life until reaching a postmenstrual age of 34 weeks or discharge. The probiotic mixture will be provided in capsules, opened, dissolved in water and given orally or via nasogastric tube, according to the feeding regime of each neonate (breast milk, donor milk or formula). Where concerns for NEC or LOS are present, probiotics will be stopped and reinstated once enteral feeds are recommenced.

Evaluation of effect of intervention

At 24 months corrected age there will be a Bayley-III scale test in an extensive examination performed by independent assessors, blinded to group allocation. After this evaluation, patients will be divided into four categories according to their degree of neurodevelopment: survival without neurodevelopment impairment (normal neurodevelopment), mild impairment, moderate impairment, or severe impairment²⁶. Mild impairment will be considered if they have muscle tone changes, impaired fine or gross motor coordination, Bayley scale score between 71-84, moderate behaviour disorders or mild visual

disability. Moderate impairment will be diagnosed when suffering from spastic diplegia, hemiplegia, seizures (non-febrile), Bayley scores between 50-70, severe behaviour disorders, moderate visual disability or mild-moderate hypoacusis. Severe impairment will be attributed to subjects with spastic quadriplegia, choreoathetosis, ataxia, Bayley score <50, blindness or severe hypoacusis.

Posteriorly, at 6 years of age, we will assess the presence of cerebral palsy, learning difficulties, behavioural disorders (autism spectrum, attention deficiency and hyperactivity disorder) and scores in the tests WISC-V, CBCL 6-18 and BRIEF-2. We will also perform a semi-structured interview to parents or legal guardians to determine the degree of impairment of the child, that might have not been previously included.

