On the other hand, at 6 years of age we will proceed to sampling of blood plasma for the study of different biomarkers related to neurodevelopment, inflammation, and intestinal permeability. We will analyse the following: NeuN, Doblecortina, GFAP, GDNF, Ki67, Nrf2, BDNF, NGF, neurotrophina-1 (NT-1), neurotrophina-3 (NT-3), neurotrophina-4 (NT-4), DYRK1A, HIF1 α , S100B i GSK3B. Regarding inflammation we will assess IL1B, IL6, IL8, IL10, IL12, TNF- α . We will finally determine presence of lipopolysaccharide in plasma with an ELISA.

7 Statistics

Considering an alpha risk of $\alpha = 0.05$ and a beta risk of $\beta = 0.2$ in a bilateral contrast, a minimum of 90 subjects in each group were required to detect a statistically significant difference between groups, where for the control group the proportion of some neurodevelopmental alteration was expected to be at least 0.4 and for the group treated with probiotics at least 0.2.

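### The day-7 start of treatment limits survival but not NEC, late-onset sepsis or IVH, so their relative risks can include events before exposure; section 3 also words the groups by receipt in a sequential design

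*Protocol*

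**What the plan says.** - **Comparison.** Protocol section 3 states that NEC, late-onset sepsis, IVH and "mortality of premature infants will also be assessed comparing those neonates that received probiotics from those that did not".
- **Outcome list.** Section 3.1 lists "Necrotising enterocolitis, early and late-onset sepsis, mortality" and, separately, "Intraventricular haemorrhage (I-IV". It gives no time window for any of them, and no day that divides early from late sepsis.
- **Design.** Section 4 calls the trial a "Quasi-experimental, sequential, unicentric, cohort study". Section 5 covers births from 2014 to 2019 and adds: "There will be a 12 month wash out period (year 2017) to alleviate cross contamination of probiotics". Together these imply one cohort born before 2017 and one born after, but no sentence ties the groups to those periods or says which is the probiotic period.
- **Landmark.** Section 5.1: "Participants will have to survive beyond 7 days of life (moment where the probiotic intervention will be given". Section 6 has the product given "from 7 days of life until reaching a postmenstrual age of 34 weeks or discharge".
- **Group wording elsewhere.** The sample size paragraph of section 7 has a control group and gives an expected proportion "for the group treated with probiotics at least 0.2".
- **Analysis.** Section 7.2 applies a relative risk with 95% confidence interval to dichotomous variables in general.

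**The concern.** The protocol recognises day 7 as the start of exposure and protects mortality with it, since every infant analysed has survived past that day. NEC, IVH and possibly late-onset sepsis have no such protection. An IVH or NEC in the first days of life precedes the first dose, yet as written it counts in a relative risk that will be read as an effect of the product. The protocol's second hypothesis claims reductions in exactly these outcomes.

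The wording of the groups is a lesser, related matter. If groups follow birth period, an infant of the probiotic period who never starts stays in the probiotic group. If groups follow receipt, that infant moves to the untreated group. When the reason for not starting is an early event, exposure then depends on the outcome.

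**Working it through.** **The plan's own figure.** For 0.4 versus 0.2, two-sided 0.05 and 80% power, the pooled two-proportion formula gives 82 per group, or 91 with continuity correction, against the stated 90. That figure concerns neurodevelopmental alteration and does not depend on anything below.

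**Inputs.** From the protocol: 90 per group, two-sided 0.05, treatment from day 7. Assumed, because the protocol gives no risks or timing for these outcomes: control risk from birth c = 0.20, share f of control events before day 7, true relative risk after day 7 of 0.50.

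**1. Groups by period, equal early risk.** Counted from birth, RR = f + (1 − f) × 0.50.

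| f | RR from birth | Power from birth, normal (exact) | Power from day 7, normal (exact) |
|---|---|---|---|
| 10% | 0.10 + 0.45 = 0.55 | 38% (38.4%) | 42% (42.5%) |
| 50% | 0.50 + 0.25 = 0.75 | 14% (14.0%) | 25% (24.0%) |
| 90% | 0.90 + 0.05 = 0.95 | 4% (5.2%) | 8% (4.6%) |

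Power from birth compares 0.20 with 0.20 × RR. Power from day 7 compares 0.20(1 − f) with half of it, keeping all day-7 survivors in the denominator. The normal figures use the pooled-variance approximation; the exact ones enumerate the uncorrected chi-square test.

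**2. Groups by period, unequal early risk.** Take f = 30%. The control group has early risk 0.06 and later risk 0.14; the probiotic group has later risk 0.07 at a true RR of 0.50, or 0.14 with no effect.

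| Early risk, probiotic period | RR from birth, true RR 0.50 | RR from birth, no effect |
|---|---|---|
| 0.02 | 0.09/0.20 = 0.45 | 0.16/0.20 = 0.80 |
| 0.03 | 0.10/0.20 = 0.50 | 0.17/0.20 = 0.85 |
| 0.06 (equal) | 0.13/0.20 = 0.65 | 0.20/0.20 = 1.00 |
| 0.12 | 0.19/0.20 = 0.95 | 0.26/0.20 = 1.30 |

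Dilution towards 1 therefore holds only under equal early risk.

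**3. Groups by receipt, read literally.** Same inputs, equal period sizes, equal early risk e = 0.06, later probiotic risk l. Let m be the share of probiotic-period infants with an early event who never start. Then RR = [(e(1 − m) + l)/(1 − em)] ÷ [(c + em)/(1 + em)].

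| m | True RR 0.50 (l = 0.07) | No effect (l = 0.14) |
|---|---|---|
| 0% | 0.65 | 1.00 |
| 25% | 0.55 | 0.89 |
| 50% | 0.46 | 0.79 |
| 100% | 0.30 | 0.61 |

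For example, m = 50% gives (0.10/0.97)/(0.23/1.03) = 0.46. The bias changes sign at about m = 39%. Nothing in the protocol informs m, so this shows only that neither direction nor size is fixed.

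**The case against.** **Event windows and analysis sets are often left to a SAP.** That is true, and silence alone would be no finding. But this protocol itself fixes a landmark for one outcome, omits it for its neighbours, and words the groups in a way its design does not match. That part stands as a fault of the text.

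**A reader might infer that the plan does group by receipt and will favour the product.** The documents do not support this. Section 3 goes on to speak of two groups, section 6 of assessors blind to group allocation, and section 7 of a control group and a treated group, so the verb in section 3 may be shorthand. No passage describes an infant who never starts. The rule in section 6 for stopping and reinstating the product does not itself create one, and it gives no reason why IVH would prevent a start. The low values in the receipt table need a large share of early-event infants never to start.

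**A reader might also infer that early events always dilute the effect.** This too goes beyond the documents. Birth years on either side of a wash-out year in a non-randomised design need not have the same early risk, and step 2 shows movement both ways.

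**A landmark count does not give a clean estimate.** This stands. IVH first seen after day 7 may have begun earlier. Infants with an early event also stay in the denominator: if only first events counted and early risk were 0.18 in controls and 0.09 in the probiotic group, a true 0.50 among infants still at risk would appear as 0.50 × 0.91/0.82 = 0.55.

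**Conclusion.** The timing point holds. Following the text, NEC, IVH and, depending on an unstated cut-off day, late-onset sepsis can enter the relative risk with onset before exposure. The distortion from 0.50 to 0.55, 0.75 or 0.95 is conditional on equal early risk and on assumed shares of early events; without equal risk, the direction is open. The wording by receipt is secondary: it is a real ambiguity, with a bias of unknown size and direction if taken literally.

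Mortality is already covered by the day-7 survival criterion. The neurodevelopmental outcome and the 90 per group are untouched. Severity is minor to moderate.

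**What to change.** In section 3:

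- Define the two groups by birth period, before and after the 2017 wash-out, and name the probiotic period. The investigators must confirm this, since the protocol only implies it.
- Analyse all eligible infants who survive beyond day 7 in the group of their birth period, with a comparison by receipt as secondary.
- In both groups, count NEC and late-onset sepsis episodes with onset after day 7, and IVH first seen or progressing in grade on ultrasound after day 7. Counting episodes and progression keeps new events in infants who had an earlier one.
- Report earlier events by group as baseline characteristics, where a difference cannot be a product effect and would reveal drift between periods.
- Add a sensitivity analysis excluding infants who already had the event by day 7.

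**Cost.** Onset dates must be extracted, and IVH can be dated only by ultrasound. Fewer events count: at control risk 0.20 and true RR 0.50, the expected numbers per 90 arising after day 7 are 16.2 versus 8.1, 9.0 versus 4.5, or 1.8 versus 0.9 when 10%, 50% or 90% of control events are early. Any gain in power is modest, and at 90% there is none on the exact calculation.

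Grouping by period lets non-starters dilute a real effect. With a share u never starting and k times the average risk, RR = (1 − uk) × 0.50 + uk. That is 0.525 at u = 5%, k = 1 and 0.65 at u = 15%, k = 2. Confounding by period remains whatever the window.

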3.1 Main and secondary variables

- Gestational age, weight, length and head circumference at birth
- Sex
- Multiple gestation

- Gestational pathology (diabetes, preeclampsia, maternal sepsis, placental disease, in vitro fecundation)
- IUGR and degree of IUGR
- Inborn vs Outborn
- Apgar at 5 and 10 minutes
- Antenatal steroids
- Type of delivery (vaginal vs caesarean)
- Coriamnionitis
- Type of feed (breastfeeding, donor milk or formula)
- Duration of breastfeeding
- Necrotising enterocolitis, early and late-onset sepsis, mortality
- Antibiotic use beyond 48 hours of life
- Days of parenteral nutrition
- Days of enteral nutrition
- Days of invasive ventilation, days of non-invasive ventilation, days of oxygen
- Days of stay in intensive care
- Chronic lung disease
- Intraventricular haemorrhage (I-IV)
- Periventricular leukomalacia
- Cranial ultrasound result
- Retinopathy of prematurity
- Neurosensorial hearing loss
- Cerebral palsy
- Colic in early infancy
- Bayley score at 2 years of age
- MRI at 2-3 years of age
- Growth chart
- Moment of “catch-up”
- Childhood diseases (asthma, atopic skin, hospital admissions, allergy,...)
- Need for antibiotics or probiotics during childhood >48 hours
- Weight and height at the assessment
- WISC-V at 6 years
- CBCL 6-18 (Child Behaviour Checklist 6-18)
- BRIEF-2
- Mother tongue
- Parental age
- Cultural level of parents
- Ethnical origin
- Parents work
- Kind of family (single parent, ...)
- Social services requirements
- Need to attend early stimulation centre

4 Study design

Quasi-experimental, sequential, unicentric, cohort study with the performance of neuropsychological tests and biomarkers of neurodevelopment, inflammation, and intestinal permeability.

We estimate an initial phase of 2 years with a comparison at 6 years of age (4 years after start of trial).

5 Enrolment of participants

Infants born below 32 weeks gestational age and birth weight under 1500g cared for at BCNatal Hospital Clínic (tertiary neonatal unit) in Barcelona between January 2014 and December 2019. There will be a 12 month wash out period (year 2017) to alleviate cross contamination of probiotics.

Participants will be contacted via phone (parent/legal guardian) for those that consented to be included for a 6-year assessment and blood sampling. In those cases where contact via phone has not been possible, contact to reference Paediatrician will be sought.

